1. INTRODUCTION AND BACKGROUND

Cross-linking (CXL), a process by which collagen fibrils form covalent bonds with adjacent molecules, was first discovered in the corneas of diabetic patients who cross-link through glycosylation and have a decreased incidence of keratoconus.¹ It is currently used as a treatment for corneal ectatic disorders such as keratoconus and post-LASIK ectasia. CXL involves applying riboflavin to the cornea and photo-chemically activating it with UV light. This has been shown to strengthen the cornea and allow it to retain its normal shape.¹-⁴ There has been recent interest in corneal CXL as an adjuvant therapy for infectious keratitis.⁵ There are two mechanisms by which CXL may benefit patients with infectious corneal ulcers; antimicrobial effects, and increased resistance of corneal tissue to enzymatic degradation.

In vitro efficacy of UV-A + riboflavin against the most common bacterial ocular pathogens, such as *Pseudomonas aeruginosa* and *Streptococcus pneumonia* has been demonstrated.⁶ In addition to these *in vitro* data, multiple case reports have suggested potential benefits of collagen CXL for treatment of bacterial and fungal keratitis, such as symptomatic improvement, resolution of resistant infection, and halting of progressive melting.⁷⁻¹⁰ One small study treated a series of patients with bacterial keratitis exclusively with photo-chemically activated riboflavin, which resolved infection in all patients.¹¹ Interestingly, only 2 of the 16 study participants required topical antibiotic treatment. *Thus, riboflavin + UV-A could potentially decrease antibiotic resistance and ocular surface toxicity that can complicate the current management of bacterial keratitis.*

Filamentous fungal corneal ulcers continue to have a poor prognosis and further investigation into their treatment is warranted. Unfortunately, *in vitro* collagen CXL alone has failed to demonstrate fungal pathogen inactivation.^{6,12} However, one study showed improved inhibition of fungus *in vitro* with amphotericin plus riboflavin+UV-A compared with amphotericin alone.⁶ The authors suggest that CXL may improve diffusion of antifungal medications or inhibit fungal proliferation through more complex mechanisms. Although the evidence for cross-linking as a treatment for fungal keratitis is less robust, clinicians have already begun using UV-A + riboflavin in conjunction with antifungals in hopes that there will be some benefit in this challenging disease. Thus, scientific investigation into this treatment approach is necessary.

Research Question: Is collagen cross-linking a useful adjuvant in the treatment of infectious corneal ulcers?

1.1 Specific Aims:

- 1. To determine if patients with culture positive bacterial and fungal keratitis clear their repeat cultures more quickly with the addition of collagen cross-linking.
 - We hypothesize that there will be an increased rate of negative cultures immediately post procedure in the CXL group compared with sham CXL.
- 2. To determine if CXL can decrease enzymatic degradation and prevent corneal thinning and perforation.
 - Hypothesis 2A) There will be a decreased rate of perforation among study participants treated with CXL.
 - Hypothesis 2b) There will be less corneal thinning as measured by optical coherence tomography in the CXL group at 3 months.
- 3. To determine what effect CXL has on visual acuity, corneal astigmatism, and 3-month infiltrate/scar size.

- Hypothesis 3A) There will be improved visual acuity with reduced 3-month infiltrate/scar size among study participants treated with CXL.
- Hypothesis 3B) There will be no difference in irregular astigmatism (as measured by topography) between participants in the CXL group versus antibiotics alone.

1.2 Study Outcomes:

Primary Outcome:

- Microbiological cure on repeat culture
 - o CLAIR I. Bacterial ulcers Culture at 4 hours
 - o CLAIR II Fungal ulcers Culture at 24 hours

Secondary Outcomes:

- BSCVA at 3 months
- Scar size/depth, as measured by clinical exam, slit lamp photographs and OCT
- Adverse events including rate of perforation/need for TPK
- Thinning as measured by pachymetry and OCT
- Topography and corneal higher-order aberrations
- Change in IND-VFQ from baseline to 3 months.

1.3 Study Design:

Cross-Linking Assisted Infection Reduction (CLAIR) I for bacterial ulcers and CLAIR II for fungal ulcers is a series of randomized, masked, clinical trials. The purpose of these studies is to determine differences in microbiological cure for 1-day repeat cultures between different medical antimicrobial treatments alone versus antimicrobial treatment plus collagen cross-linking. There will be 1:1 randomization to each of these treatment groups:

CLAIR I. Bacterial Ulcers:

- 1) Topical 0.5% Moxifloxacin alone
- 2) Topical 0.5% Moxifloxacin plus cross-linking

CLAIR II. Fungal Ulcers:

- 1) Topical 5% natamycin alone
- 2) Topical 5% natamycin plus cross-linking
- 3) Topical 0.15% amphotericin alone
- 4) Topical 0.15% amphotericin plus cross-linking

2. ORGANIZATION

Aravind Eye Hospital, Madurai along with the University of California San Francisco (UCSF) will jointly execute these clinical trials. Aravind Eye Hospital will mainly be responsible for recruitment and enrollment, intervention implementation, and follow-up visits. UCSF will take the lead on all data analysis, writing of study-related materials, and writing journal publications.

2.1 Collaborating Institutions:

Aravind Eye Hospital, India

Dr. [name] will be the lead investigator at Aravind Eye Hospital. All recruitment, treatment/intervention, and follow-up visits will be done at the Aravind Eye Hospitals. All study personnel assisting with the research will be adequately informed about the protocol, the research procedures, and their duties and functions through ongoing communication between the 2 sites.

Aurolab at Aravind Eye Hospital in Madurai will be responsible for preparing and distributing study medications. The microbiology lab in Madurai will perform the cultures and serve as a bank for all specimens collected. Madurai microbiology lab will serve as a reference lab that will assist with any difficult microbiological identification.

Francis I. Proctor Foundation, University of California, San Francisco, USA

The Proctor Foundation is an organized research unit at the University of California, San Francisco. The Foundation has a 56-year history of research in ocular infectious and inflammatory disease and runs one of the leading corneal fellowship training programs in the United States. Proctor Foundation faculty have been involved in prevention of blindness research in developing countries since the Foundation's inception. The impetus for establishing the Foundation in 1947 was to eradicate trachoma in the American Southwest and other parts of the world.

3. PATIENT FLOW

3.1 Study Timeline

When the patient presents to clinic with infectious keratitis and undergoes corneal scraping by the treating ophthalmologist, a specimen will be submitted for microbiological testing (KOH and Gram stain bacterial or fungal). This is a routine practice already in place at the hospital. If the patient has a positive KOH or Gram stain, the patient will be approached by study personnel to be enrolled in study.

If enrolled, study subjects will follow the procedures below - if bacteria positive on Gram stain, the subject will undergo procedures outlined for CLAIR I. Bacterial ulcers; if positive for fungus on KOH, subject will undergo procedures outlined for CLAIR II. Fungal ulcers.

Study participants will be required to have 4 follow-up visits, one for the cross-linking procedure and re-scraping, one at 3 days for re-scraping, one at 3 weeks (2.5 – 5 weeks) and one at 3 months (visit window: 2.5 -3.5 months). Additional visits may be needed and will be determined by the physician/investigator.

3.3 Randomization

Each study eye will be randomly assigned to the treatment group. Block randomization will be performed using a computer program (Statistical package R; Version 2.12; R Foundation for Statistical Computing, Vienna, Austria) by the coordinating site.

Once an eye is enrolled in the study, the study coordinator will assign the study participant's eye an ID (alphanumeric code) and organize the procedure in the operating room within 3 hours for bacterial ulcers, and within 24 hours for fungal ulcers. Once the study participant has been assigned a study participant ID and randomized to treatment group, they will be included in the intention to treat analysis.

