3.4 Study visits

3.3.1 Baseline Visit. During this visit, eligible patients will be enrolled in the study and will give consent. The baseline patient form will be completed and baseline topography will be obtained.

CLAIR I. Bacterial Ulcers:

Study participants will be randomized to one of two possible treatment arms: 1) topical 0.5% moxifloxacin alone 2) topical 0.5% moxifloxacin plus CXL. Those randomized to CXL will undergo the procedure in the operating theatre within 4 hours. Both arms will undergo repeat scraping at 4 hours post enrollment. Thereafter, all study participants will start 0.5% moxifloxacin every hour. All patients will be admitted to the inpatient setting until the 3^{rd} day.

CLAIR II. Fungal Ulcers:

They will be randomized to one of four possible treatment arms 1) topical 5% natamycin alone, 2) topical 5% natamycin plus CXL, 3) topical 0.15% amphotericin alone or 4) topical 0.15% amphotericin plus CXL. All study participants will begin medical therapy immediately (either natamycin or amphotericin) every hour and those randomized to CXL will undergo the procedure in the operating theatre within 24 hours. All study participants will undergo repeat scrapping at 24 hours from enrollment. All patients will be admitted to the inpatient setting until the 3^{rd} day.

- *3.3.2 Procedure visit.* All study participants randomized to CXL will have the procedure in the operating theater. This will occur within 4 hours for bacterial ulcers and within 24 hours of the baseline visit for fungal ulcers. Once a study participant has been randomized to treatment, he will have the treatment even if there is a delay in the operating theatre that results in delayed treatment, however re-scraping will occur at 4 hours for bacterial ulcers and 24 hours for fungal ulcers even if they have not yet had cross-linking. If the cross-linking occurs after repeat scrapping, a third smear and culture should be performed.
- *3.3.3 Day 3 visit.* During this visit, study participants will have BSCVA recorded, IND-VFQ, slit lamp examination and undergo repeat scraping and culture of the corneal ulcer. Thereafter, all additional treatments including but not limited to topical antimicrobials, or oral antimicrobials, will be at the clinician's discretion. At this point patients may be discharged from the inpatient setting.
- 3.3.4 *3 week visit.* During this visit study participants will have BSCVA recorded, slit lamp examination, and they will have digital photography.

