4.2.2 Collagen Cross-Linking

All study participants randomized to collagen cross-linking will have cross-linking within 4 hours for bacterial ulcers and within 24 hours for fungal ulcers. They will be taken to the operating theatre and the procedure will be performed under sterile conditions.

Cross-linking will be performed as follows:

- A drop of topical anesthetic (0.5% tetracaine or 4% lidocaine) is administered to the eye.
- A 30-minute loading dose of 0.1% topical riboflavin and 20% dextran T500 drops will be administered every 2 minutes.
- The cornea will be exposed to UV-A light at a wavelength of 365nm with irradiance of 3mW/cm² for a total of 30 minutes.
- Throughout the UV-A treatment the study participant will continue to receive topical riboflavin Q5 min intervals during treatment.
- The study participant will be transferred back to the microbiology laboratory for repeat scraping and culture (see section 4.4.1).

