#### SPECIFIC AIM 1 analysis:

CLAIR I Bacterial Trial: McNemar's two-sample paired-proportions test will be used to compare pre- and post- cross-linking cultures on smear-positive bacterial corneal ulcers. In order to detect a 30% difference in repeat culture status (80% in the control group vs. 50% in the crosslinking group), we would need to enroll 78 study participants, assuming a significance level of 0.05 and no loss to follow-up (since the primary outcome occurs the same visit as enrollment).

CLAIR II Fungal Trial: Given the 4 arms of the trial, we have estimated a sample size based on a significance level of 0.0125. In order to detect a 30% difference (80% in control versus 50% in the crosslinking group), we would need to enroll 110 study participants. This assumes no loss to follow-up, since the primary outcome occurs at the same visit as enrollment. In reality, we should have more statistical power since we will also take into account the results of the baseline culture, which we expect to be highly correlated with the follow-up culture.

1 | Page Version 1.4

SPECIFIC AIM 2 analysis: 3-month best spectacle-corrected visual acuity (BSCVA) will be examined in a multiple linear regression model with terms for treatment (dichotomous variable for bacterial and 4-level categorical variable for fungal ulcers) and baseline BSCVA. Similar to above, for the fungal ulcers we will first test for an overall difference between the 4 groups, then pairwise comparisons as indicated, using a Bonferroni correction. 3 and 12-month best spectacle-corrected visual acuity (BSCVA) will be examined in a repeated measures multiple linear regression model with terms for treatment (dichotomous variable for bacterial ulcers and 4-level categorical variable for fungal ulcers) and baseline BSCVA. Similar to above, for the fungal ulcers we will first test for an overall 12-month BSCVA difference between the 4 groups, then pairwise comparisons as indicated, using a Bonferroni correction.

For study participants who experience perforation or undergo therapeutic penetrating keratoplasty (TPK) this will be noted and a BSCVA will be performed prior to performing further surgery. This last observation will be carried forward (LOCF) as the 3-month BSCVA. An enhanced analysis using standard longitudinal modeling methods will be used to handle data from study participants who are lost to follow up. Additional secondary analyses will include:

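### CLAIR I gives the cross-linking window as 3 hours in one place and 4 hours elsewhere, without saying start or completion; if 4 hours limits the start, compliant eyes can have the primary culture before cross-linking is complete

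*Protocol*

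**What the plan says.** **The window.** Protocol section 3.3 has the study coordinator "organize the procedure in the operating room within 3 hours for bacterial ulcers, and within 24 hours for fungal ulcers". Section 3.4 gives a different figure for CLAIR I, under the baseline visit ("Those randomized to CXL will undergo the procedure in the operating theatre within 4 hours") and again under the procedure visit ("This will occur within 4 hours for bacterial ulcers and within 24 hours of the baseline visit for fungal ulcers"). Section 4.2.2 agrees with section 3.4: "All study participants randomized to collagen cross-linking will have cross-linking within 4 hours for bacterial ulcers and within 24 hours for fungal ulcers". The fungal window is 24 hours throughout.

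**The primary culture.** Section 1.2 sets the CLAIR I primary outcome as "CLAIR I. Bacterial ulcers Culture at 4 hours". Section 3.4 fixes the clock: "Both arms will undergo repeat scraping at 4 hours post enrollment".

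**Late procedures.** Under the procedure visit, section 3.4 foresees delay in theatre. The patient is still treated, "however re-scraping will occur at 4 hours for bacterial ulcers and 24 hours for fungal ulcers even if they have not yet had cross-linking". If CXL then follows the scrape, a third smear and culture is taken. Section 3.3 keeps every randomised participant in the intention-to-treat analysis.

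**The procedure.** Section 4.2.2 describes 30 minutes of riboflavin loading and 30 minutes of UV-A, followed by transfer to the microbiology laboratory for the repeat scrape.

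**The sample size.** The SAP's Specific Aim 1 analysis reads: "In order to detect a 30% difference in repeat culture status (80% in the control group vs. 50% in the crosslinking group". It arrives at 78 participants at a 0.05 significance level with no loss to follow-up.

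**The concern.** The CLAIR I window carries two figures, and the difference between them, one hour, equals the minimum length of the procedure. That matters because the primary culture is taken at a fixed 4 hours. Depending on how the window is read, an eye may have been fully cross-linked, partly cross-linked or not cross-linked at all when its primary outcome is measured.

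The delay rule covers eyes held up in theatre. The ambiguity adds another group: eyes with no delay and no deviation that are cultured before CXL is complete because the rule, read as a start limit, allows it. Intention to treat rightly keeps them in the CXL arm, so they pull the two arms together. Unless start and end times are recorded, a null CLAIR I result could not be separated from an outcome measured too early.

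**Working it through.** **1. Timing.** The clock is taken to run from enrollment for both the window and the scrape. The protocol says so for the scrape and implies it for the window.

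- Minimum procedure length: 30 + 30 = 60 minutes. Transfer time is not stated.
- Start at hour 3: CXL ends at hour 4 at the earliest, which leaves 0 minutes for transfer.
- Start after hour 3: CXL ends after hour 4, so it cannot be complete at the primary culture.
- Completion by hour 4: latest start = 4 − 1 = hour 3.

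| Reading of the CLAIR I limit | Latest compliant start | CXL complete at the 4-hour culture? |
|---|---|---|
| Completed within 4 hours | hour 3 | Yes at the limit, with no time for transfer |
| Started within 3 hours | hour 3 | Same as above |
| Started within 4 hours | hour 4 | Not for starts after hour 3; latest end is hour 5 or later |

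The first two rows coincide. Only the third lets a compliant eye be cultured before completion. Theatre delay can produce early cultures under any of the three.

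**2. Reproducing 78.** Inputs from the SAP: p1 = 0.80, p2 = 0.50, significance level 0.05, 1:1 allocation. The SAP states neither power nor sidedness; 80% and two-sided are assumed. With p̄ = 0.65, the usual formula for two independent proportions is

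n per arm = [1.96·√(2p̄(1−p̄)) + 0.8416·√(p1(1−p1) + p2(1−p2))]² / (p1−p2)²

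= [1.96·√0.455 + 0.8416·√0.41]² / 0.09 = (1.322 + 0.539)² / 0.09 = 38.5, rounded up to 39.

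The total is 78, an exact match. The same formula at 0.0125 gives the SAP's 110 for CLAIR II, which supports the assumed 80% and two-sided test. Power at 39 per arm is Φ[(0.30·√39 − 1.322)/0.640] = 80.5%.

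**3. Cost of early cultures.** Let f be the share of CXL-arm eyes cultured before CXL is complete. The documents give no value for f. Assume that those eyes have the control rate. The CXL-arm rate is then 0.50 + 0.30f and the difference is 0.30(1 − f).

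| f (assumed) | CXL-arm rate | Difference (points) | Power at 78 | Total for 80% power |
|---|---|---|---|---|
| 0 | 50.0% | 30.0 | 80.5% | 78 |
| 5% | 51.5% | 28.5 | 76.6% | 86 |
| 10% | 53.0% | 27.0 | 72.3% | 94 |
| 20% | 56.0% | 24.0 | 62.7% | 118 |
| 25% | 57.5% | 22.5 | 57.5% | 132 |

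The 25% row is what the start-within-4-hours reading would give if starts were spread evenly over hours 0 to 4: (4 − 3)/4 = 25%. That spread is hypothetical.

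**The case against.** The strongest reply is that the sections need not conflict. Section 3.3 describes the coordinator arranging theatre, while sections 3.4 and 4.2.2 describe patients having the procedure. A theatre slot by hour 3 plus a one-hour procedure gives completion by hour 4, just in time for the scrape. Section 3.4 also treats CXL after the scrape as an exception, which fits a completion limit. This stands as a plausible reading, but nothing in the documents selects it.

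A reader might infer that only the 3-hour figure delivers the contrast behind the sample size. The documents do not support that. A 4-hour completion limit implies the same latest start, a start at hour 3 leaves no time for transfer, and theatre delay is allowed under either figure.

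Other replies stand in part:

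- **The problem is a window equal to the culture time, and CLAIR II has that too at 24 hours.** True if 24 hours is also a start limit. The conflicting figures are confined to CLAIR I, but one definition of start or completion would serve both trials.
- **The protocol provides for late CXL through the third culture.** It does, but neither document says what that culture is for in the analysis.
- **The control rate for affected eyes is a worst case.** Agreed. An eye started at 3 h 10 min would have had full loading and 20 minutes of UV-A by hour 4.
- **The SAP names McNemar's test.** It does, while 78 matches an independent two-proportion formula, so the power figures belong to that formula.
- **The SAP plans a masked sample-size re-evaluation.** It looks at repeat-culture positivity without regard to arm, so it cannot isolate this dilution.

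**Conclusion.** The point holds as an unresolved ambiguity in a rule that the CLAIR I primary outcome depends on. The figures differ between section 3.3 and sections 3.4 and 4.2.2, start or completion is undefined, and under one open reading a fully compliant eye can be cultured before CXL is complete and be analysed as cross-linked. The calculation for 78 makes no allowance for such eyes or for delayed ones.

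A reader might also infer that CLAIR I has about 57% power. The documents do not support that either. The figure needs a 25% affected share that appears nowhere in them, the control rate in every affected eye, and a power target of 80% that is inferred rather than stated. The supportable statement is the range: on those assumptions power falls from 80.5% to 72% if 10% of CXL eyes are affected and to 63% if 20% are. If nearly all procedures finish before the scrape, the loss is small. This review takes no position on which window is right.

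**What to change.** 1. Reconcile Protocol sections 3.3, 3.4 and 4.2.2 to one CLAIR I window, chosen by the sponsor and investigators, and state whether it limits the start or the completion of CXL.
2. Check the chosen rule against the minimum 60-minute procedure, the transfer to the laboratory and the 4-hour culture.
3. Record CXL start and end times, and report the share of CXL-arm eyes cultured before completion.
4. State in the SAP that the 4-hour culture, analysed as randomised, is primary, and that the third culture is supportive.
5. If compliant eyes can still be cultured before completion, restate the detectable difference or the power for 78, with the assumed affected share.

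The cost is a short clarification in three sections and the SAP, two times on the procedure form, and possibly a less favourable power statement. No extra patients or visits are needed.

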3.4 Study visits

3.3.1 Baseline Visit. During this visit, eligible patients will be enrolled in the study and will give consent. The baseline patient form will be completed and baseline topography will be obtained.

CLAIR I. Bacterial Ulcers:

Study participants will be randomized to one of two possible treatment arms: 1) topical 0.5% moxifloxacin alone 2) topical 0.5% moxifloxacin plus CXL. Those randomized to CXL will undergo the procedure in the operating theatre within 4 hours. Both arms will undergo repeat scraping at 4 hours post enrollment. Thereafter, all study participants will start 0.5% moxifloxacin every hour. All patients will be admitted to the inpatient setting until the 3^{rd} day.

CLAIR II. Fungal Ulcers:

They will be randomized to one of four possible treatment arms 1) topical 5% natamycin alone, 2) topical 5% natamycin plus CXL, 3) topical 0.15% amphotericin alone or 4) topical 0.15% amphotericin plus CXL. All study participants will begin medical therapy immediately (either natamycin or amphotericin) every hour and those randomized to CXL will undergo the procedure in the operating theatre within 24 hours. All study participants will undergo repeat scrapping at 24 hours from enrollment. All patients will be admitted to the inpatient setting until the 3^{rd} day.

- *3.3.2 Procedure visit.* All study participants randomized to CXL will have the procedure in the operating theater. This will occur within 4 hours for bacterial ulcers and within 24 hours of the baseline visit for fungal ulcers. Once a study participant has been randomized to treatment, he will have the treatment even if there is a delay in the operating theatre that results in delayed treatment, however re-scraping will occur at 4 hours for bacterial ulcers and 24 hours for fungal ulcers even if they have not yet had cross-linking. If the cross-linking occurs after repeat scrapping, a third smear and culture should be performed.
- *3.3.3 Day 3 visit.* During this visit, study participants will have BSCVA recorded, IND-VFQ, slit lamp examination and undergo repeat scraping and culture of the corneal ulcer. Thereafter, all additional treatments including but not limited to topical antimicrobials, or oral antimicrobials, will be at the clinician's discretion. At this point patients may be discharged from the inpatient setting.
- 3.3.4 *3 week visit.* During this visit study participants will have BSCVA recorded, slit lamp examination, and they will have digital photography.
- 3.3.5 Final Visit. At the 3- Month visit study participants will have their BSCVA and slit lamp examination recorded, in addition to repeat topography and be administered the IND-VFQ.

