#### 1. Background

Cross-Linking Assisted Infection Reduction (CLAIR) I for bacterial ulcers, CLAIR II for fungal ulcers are two randomized, masked, clinical trials. The purpose of these studies is to determine differences in microbiological cure for repeat cultures between different medical antimicrobial treatments alone versus antimicrobial treatment plus collagen cross-linking. There will be 1:1 randomization to each of these treatment groups:

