### 2. Statistical Considerations, Sample Size

We will perform separate analyses for each specific aim for (I) the bacterial ulcers, (II) the fungal ulcers. Enrollment criteria require all study participants to have bacteria on smear from corneal scrapping. Previous studies have shown that 88% of bacterial cultures are positive when initial gram stain is positive. This is consistent with the experience of the microbiology lab at our own institution. We feel that this is a conservative estimate based on prior studies in a similar south Indian setting that have found approximately 90-95% of corneal scrapings with a positive Gram/KOH stain are also culture positive.

There is little current data to inform us about the effect of repeat scrapping on the culture status. In the Mycotic Ulcer Treatment Trial II, approximately 55% of fungal ulcers were culture positive 6 days after enrolling in the trial and receiving treatment. This is an approximately 7.5% reduction is culture positivity on average per day. If we consider initial scrapping to have a similar effect as one day of treatment, we can estimate that there would be an approximately 8% reduction in culture positivity due to repeat scraping in our trial.

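### CLAIR I names a pre/post McNemar test for a between-arm question, its stated purpose does not match a 4-hour culture taken before study moxifloxacin, and the Day-3 culture has no planned analysis

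*Protocol*

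**What the plan says.** **Timing.** Protocol 1.2 gives the primary outcome as "CLAIR I. Bacterial ulcers Culture at 4 hours". Protocol 3.4 (Baseline Visit, CLAIR I) states: "Both arms will undergo repeat scraping at 4 hours post enrollment. Thereafter, all study participants will start 0.5% moxifloxacin every hour". In CLAIR II, by contrast, the antifungal starts at once, before the 24-hour culture. The dosing table in Protocol 5.1 gives hourly moxifloxacin for 3 days without a start time, so it does not contradict 3.4.

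**Question.** The Aim 1 hypothesis (Protocol 1.1) expects an "increased rate of negative cultures immediately post procedure in the CXL group". Protocol 1.3 gives the purpose of both trials as "differences in microbiological cure for 1-day repeat cultures between different medical antimicrobial treatments alone versus antimicrobial treatment plus collagen cross-linking". SAP section 1 repeats this without the one-day label: "microbiological cure for repeat cultures between different medical antimicrobial treatments alone versus antimicrobial treatment plus collagen cross-linking". SAP section 3 bases its sample-size re-evaluation on a day-1 culture.

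**Test and sizing.** SAP section 2 says that for CLAIR I a "paired-proportions test will be used to compare pre- and post- cross-linking cultures", then sizes the trial at 78 on "80% in the control group vs. 50% in the crosslinking group". The same section expects an "approximately 8% reduction in culture positivity due to repeat scraping in our trial".

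**Day 3.** Protocol 3.1, 3.4 (Day 3 visit) and 3.5 schedule a repeat culture for everyone at Day 3. Protocol 5.1 holds medical management the same up to then, and discretionary treatment starts afterwards. The outcome list in Protocol 1.2 and the analyses in SAP section 2 do not mention this culture.

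**The concern.** Three things do not line up.

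1. A paired pre/post test does not estimate the difference between randomised arms. It also credits to CXL any fall in positivity that would have happened anyway, and the SAP itself expects such a fall from scraping alone.
2. With the primary culture scheduled before study moxifloxacin, the 4-hour contrast is CXL plus repeat scraping versus repeat scraping. A positive result could be reported, in the words of the stated purpose, as better microbiological cure when CXL is added to moxifloxacin. The 4-hour culture cannot show that.
3. The one culture that could speak to cure on study drug is collected from every eye but has no planned use. An analysis added after results by arm are known would be post hoc.

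**Working it through.** **1. Reproduce the 78.** Inputs (SAP section 2): 80% versus 50% positive, significance level 0.05, 1:1 allocation. Power and sidedness are not stated for CLAIR I; 80% and two-sided are assumed. For two independent proportions with pooled variance under the null (mean proportion 0.65):

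n per arm = [1.96 × √(2 × 0.65 × 0.35) + 0.8416 × √(0.80 × 0.20 + 0.50 × 0.50)]² / 0.30² = (1.322 + 0.539)² / 0.09 = 38.5, rounded up to 39, or 78 in total. Power at 39 per arm is 80.5%.

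Other standard settings of this formula miss: one-sided gives 62, continuity correction 90, 85% power 88 and 90% power 104. The 78 is therefore a between-arm sample size. Its 80% control rate equals 88% baseline positivity minus 8 points for scraping, with no term for moxifloxacin. The sizing thus agrees with a 4-hour control arm not yet on study drug.

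**2. False positives from the paired test.** Assume it is run in the 39 CXL eyes, CXL has no effect, and positivity falls by a net 8 points from scraping. Let b be the number of eyes changing from positive to negative and c the reverse. McNemar's statistic is (b − c)²/(b + c).

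In the simplest case c = 0 and b is binomial(39, 0.08), with mean 39 × 0.08 = 3.1. The uncorrected test rejects from b = 4 (4 > 3.84), although the exact p-value there is 2 × 0.5⁴ = 0.125. The exact test needs b = 6 (2 × 0.5⁶ = 0.031). The probabilities are P(b ≥ 4) = 0.381 and P(b ≥ 6) = 0.088.

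| Positive to negative | Negative to positive (assumed) | Uncorrected | Exact or continuity-corrected |
|---|---|---|---|
| 8% | 0% | 38.1% | 8.8% |
| 10% | 2% | 29.4% | 10.5% |
| 12% | 4% | 22.3% | 10.8% |

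**3. A between-arm test at the same N.** SAP section 2 gives baseline positivity of 88%, or 90-95% in similar settings. About 78 × 0.05 = 3.9 to 78 × 0.12 = 9.4 eyes would then be baseline-negative. A Mantel-Haenszel risk difference stratified by baseline culture (Sato variance, 40,000 simulated trials, baseline-negative eyes assumed to stay negative, which is the best case) has power of about 0.93, 0.91 and 0.86 at baseline positivity of 88%, 90% and 95%. Its simulated type I error is about 0.054-0.060, slightly above nominal.

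**4. Day 3.** The documents give no Day-3 bacterial culture rate, so the control rates below are assumed, with the planned ratio 50/80 = 0.625 carried over. The unadjusted 95% CI half-width is 1.96 × √[(p₁q₁ + p₂q₂)/39].

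| Control positive | CXL positive | Power, 39 per arm | CI half-width |
|---|---|---|---|
| 70% | 43.75% | 65% | 21 points |
| 50% | 31.25% | 39% | 21 points |
| 30% | 18.75% | 21% | 19 points |

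**The case against.** The strongest reply is that the 4-hour design is coherent. The Aim 1 hypothesis, the primary outcome and the sizing all describe an immediate contrast with no drug effect, and only a summary sentence shared by both trials reads otherwise. That stands. A reader might infer that the primary comparison is invalid or that the design cannot test CXL, and the documents do not support this. The 4-hour culture is taken in both arms on the same clock, even if CXL is delayed, and every randomised eye is in the intention-to-treat analysis. The purpose point is a conflict of wording that limits the conclusion.

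A reader might also infer that nothing in the plan addresses adjuvant benefit. That goes too far: the 3-month visual acuity, scar, thinning and perforation outcomes do. The gap is confined to microbiological cure on study drug.

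On the test, it can fairly be said that 22-38% overstates the error. Those figures come from the uncorrected statistic with about three expected discordant eyes; exact or continuity-corrected versions give 9-11%. The SAP also does not say that the test is confined to the CXL arm, so the size of the error is conditional on that reading. The mismatch between a pre/post test and a between-arm hypothesis remains.

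On Day 3, Aim 1's interest in faster clearance and the SAP's reference to repeat cultures could loosely cover it, and power would be low. Both are true, but no analysis is specified, and low power is a reason to label the estimate rather than leave it unplanned.

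**Conclusion.** The point holds and should be fixed before any result by arm is seen.

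- **Test:** the named CLAIR I test does not answer the randomised question that the 78 was sized for. Its false-positive rate would be about 9-11% against a nominal 5% with an exact or continuity-corrected version. This rests on the test being run in 39 CXL eyes, the SAP's 8-point scraping effect, and 0 to 4 points of reverse change.
- **Purpose:** as Protocol 3.4 schedules it, the primary result supports a conclusion about the immediate effect of assignment to CXL and does not support one about cure with moxifloxacin plus CXL versus moxifloxacin alone. The passages conflict. Which schedule is intended is for the trial team to say.
- **Day 3:** a between-arm estimate is available from data already scheduled, but power is only about 21-65% under the assumed rates, so a null result would be inconclusive.

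The sample size is not in error: 78 reproduces on its own inputs and suits the between-arm test.

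**What to change.** **(a) Primary test, SAP section 2.** Replace the paired test for CLAIR I with a comparison between randomised arms of 4-hour culture positivity in all randomised eyes, with a 95% CI, adjusted for or stratified by baseline culture. If a Mantel-Haenszel risk difference is chosen, state its slight type I inflation (about 0.054-0.060 in simulation) or take the p-value from an exact stratified test. N stays at 78.

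**(b) Purpose and timing.** The trial team must reconcile Protocol 1.3 and 3.4 with SAP sections 1 and 3 on drug start, culture time, the one-day labels and the stated purpose. No schedule is proposed here. While Protocol 3.4 stands as written, limit the primary conclusion to the immediate effect of assignment to CXL.

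**(c) Day 3.** Add CLAIR I Day-3 culture positivity by randomised arm to the secondary outcomes and analyses: risk difference with 95% CI, adjusted as in (a). Report missing cultures by arm. Bound the result by opposite assignments: missing CXL cultures positive with missing control cultures negative, then the reverse. Giving both arms the same value would not bound the difference. State in advance that power is low and a null result is inconclusive.

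**(d) Delayed CXL.** Report how many CXL eyes had the 4-hour culture before CXL. Treat the third culture as descriptive, because only CXL-arm eyes can have it and it may fall after moxifloxacin has started.

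**Cost.** Wording changes in both documents and one change of named test, with no new visits, cultures or participants. The downsides are one more low-powered secondary analysis and a possible small Day-3 bias towards CXL, since eyes with delayed CXL receive an extra scraping.
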